2.6. Recruitment Status

Not recruiting

2.7. Study Timeline

Study timelines have been attached to the end of this protocol; the first timeline documents study activities by wave ([Figure 1](#), pg. 36).

2.8. Enrollment of First Subject

03/18/2020

Table 1. Inclusion Enrollment Table for RADx Participants

	Hispanic Ethnicity													
	Hispanic or Latino (n = 334)				Not Hispanic or Latino (n = 140)			Prefer not to answer / Unknown (n = 12)						
	Gender Identity Categories				Gender Identity Categories			Gender Identity Categories						
	Man	Wo man	Non- binary/ Other	Prefer not to answe r	Ma n	Wom an	Non- binary/ Other	Man	Wom an	Non- binary/ Other	Unkno wn	Total		
Racial Categories														
American Indian/Alaska Native	9	1	1	0	1	1	0	2	0	0	0	15		
Asian	2	0	0	0	1	1	0	0	0	0	0	4		
Native Hawaiian or Other Pacific Islander	4	0	0	0	0	0	0	0	0	0	0	4		
Black or African American	23	6	0	0	44	22	3	2	1	0	0	101		
White	19	13	1	0	30	25	1	2	0	0	0	91		
Some other race	138	29	3	0	3	2	0	3	0	0	0	178		
More than one race	11	6	1	0	2	2	0	1	0	0	0	23		
Prefer not to answer	44	5	0	1	1	0	0	0	0	0	0	51		
Unknown	14	3	0	0	1	0	0	0	0	0	1	19		
Total	264	63	6	1	83	53	4	10	1	0	1	486		

Table 2. Inclusion Enrollment Table for Staff Participants

Racial Categories	Ethnic Categories				Total	
	Not Hispanic or Latino		Hispanic or Latino			
	Female	Male	Female	Male		
American Indian/Alaska Native	0	0	0	0	0	
Asian	0	0	0	0	0	
Native Hawaiian or Other Pacific Islander	0	0	0	0	0	
Black or African American	2	1	1	2	6	
White	0	0	0	0	0	
More than One Race	0	0	1	1	2	
Total	2	1	2	3	8	

Section 3. Protection and Monitoring Plans

3.1.1(a) Human Subjects Involvement, Characteristics, and Design

Scientific Rationale for Study Design

The primary goals of this proposal are to 1) adapt and compare the efficacy of two evidence-based outreach and recruitment strategies that target and identify (reach) individuals who use opioids and other drugs to increase uptake of COVID-19 testing and related services (quarantine, treatment); and 2) document the organizational, staff and individual-level factors *that influence implementation* (i.e. *fidelity, acceptability, feasibility, sustainability*) *of the strategies* to develop a plan for dissemination and scale-up in CBOs and other settings who serve opioid and other substance using individuals in New York City. The subjects will be recruited from two areas in New York City (NYC), northern Manhattan (Washington Heights and Harlem) and the South Bronx, areas served by two community based organizations (CBOs) that specialize in SUD treatment and provide a wealth of supportive services for individuals who abuse substances: Argus and Alliance (see **Facilities and Other Resources**).

There are **three phases** to the proposed study:

- **Phase 1: Strategy Adaption**, will comprise a series of meetings (n=8) attended by a Working Group (WG) that will include n=7 members of the research team, n=10 members of the project Community Advisory Board (CAB), which will be assembled from interested members of the CABs of Argus and Alliance, and interested staff from both agencies. Using community-based participatory research (CBPR) approaches, the WG will develop protocols and materials (e.g. messaging, target locations, training protocols, visual materials) for two recruitment strategies that aim to encourage individuals who use opioids and other drugs to seek COVID-19 testing. As we will not be collecting data from WG members, nor will consent/assent be obtained for their participation, they are not considered human subjects.
- **Phase 2: Efficacy Test and Implementation Evaluation**, a trial will be performed in which the two strategies will be compared with respect to reach, testing uptake and related services; we will aim to recruit 500 participants who use opioids or other substances over an 8 month period of time (n=250 in each strategy). Participants will be assessed upon enrollment into the study. In addition, n=8 credible messengers (n=4 at each site), and n=20 staff members at each site employed at our community partners agencies Alliance and Argus, will complete baseline and 12-month follow-up surveys, fidelity/feasibility checklists, PDSA cycle and will participate in a workgroup at the completion of Phase 2.
- **Phase 3: Sustainment**, CBOs will implement the strategy proven efficacious based on outcomes, and we will examine their sustainment of the program.

- The **two recruitment strategies** used in Phase 2 are **chain referral** and **credible messenger**:
 - 1) In the **chain referral strategy**, an initial set of n=8 “seed” participants are recruitment by staff of eligible clients receiving services at Argus and Alliance (n=16 total seeds). For clinic-based recruitment of “seeds”, participants will be recruited from among those individuals who use opioids and other drugs who are receiving services through Argus or Alliance; services do not need to be substance use related. (Following a brief training, these “seed” participants then recruit additional participants (“peer recruits”) from among their own peer networks of those known to use opioid or other drugs in community settings (peer-recruitment). “Seed” participants are given three unique, numbered coupons, which they can give to people they know (peers) who are also use opioids and other drugs. The coupons will have information, by which peers who are interested in participating in the study can contact the research team to be screened for eligibility. Participants will receive renumeration for each peer recruit who enrolls in the study by redeeming a coupon given to them by that participant. Peer-recruits then repeat the same process with members of their peer network.
 - 2) The **credible messenger strategy** involves leveraging the existing infrastructure at both Argus and Alliance, which includes credible messenger programs that are well-established, with considerable influence and impact within the respective communities served by these two agencies. The credible messengers within these programs have been trained to conduct community outreach to target individuals at increased risk for HIV, STIs, HCV and SUD and encourage testing and/or linkage to services. Interested credible messengers (n=4 from each site) will serve as messengers in the current study and will be trained to also include education about COVID-19, ways to reduce risk as well as ways to increase motivation to test for COVID-19 at the respective clinics. Credible messengers will conduct community outreach, targeting those locations and venues where potentially credible participants are located, and will provide education and encourage these individuals to seek testing. The potential participants will be given a coupon which will be redeemed at the clinic when the participant is enrolled in the study after being determined as eligible.

Justification for Intervention

Social network strategies effective at identifying hidden populations and improving access to HIV related services may improve uptake of COVID-19 testing. Social network interventions utilize existing patterns of relationships to accelerate behavior change have been successful in increasing the uptake of HIV testing among marginalized populations, including people who use drugs. Moreover, social network approaches successfully counter stigma, medical mistrust, and misinformation around HIV, making them uniquely suited for addressing similar issues in the context of COVID-19. Two distinct social network recruitment strategies, chain-referral and Popular Opinion Leader (POL or “credible messenger”) models may be promising for increasing rapid COVID-19 testing. In chain-referral a discrete number of “seeds” are identified and incentivized to refer members of their social networks, who in-turn repeat the process. In POL models, popular and socially influential individuals with lived experience are trained to engage within formal and informal social networks to promote behavior change. Based on the efficacy of chain-referral and POL recruitment in the context of the HIV/AIDS epidemic, the success of these strategies to promote COVID-19 testing in underserved populations of substance users is highly plausible. Given the distinct differences of these strategies, it is important to contrast them to determine the comparative benefits of one approach over the other.

Ongoing quality improvement (QI) to promote an adaptive response to an evolving epidemic and promote sustainability. Plan-do-study-act (PDSA) is an evidence-based, rapid-cycle change model for testing enhancements on a small scale before incorporating them on a larger scale. Training staff, and POLs to use data (e.g. testing uptake, client feedback) to monitor and improve program performance may be a useful tool to develop sustainable strategies that address a rapidly changing pandemic as well as incorporate new testing, treatment and prevention (i.e., vaccine) technology.

The theoretical approach will integrate Andersen's Model, Social Cognitive Theory (SCT), and the Exploration Preparation Implementation Sustainability (EPIS) framework to understand contextual/system- and individual-level factors that influence implementation of a community outreach and testing uptake approach. Andersen's Model provides a framework to identify key domains to target when developing interventions to improve service utilization.

We propose research to establish efficacy and sustainability of a community-social network outreach model that partners infectious disease health providers with community based organizations to successfully implement (reach, uptake, delivery and sustainment) COVID-19 rapid POS testing among a highly vulnerable and often underserved population, those who use opioids and other substances. Two distinct social network recruitment strategies, found efficacious for identifying HIV+/high risk populations and increasing uptake of HIV testing (cites) will be adapted and compared. Guided by the EPIS framework, SCT, and Andersen's model, this 2-year study will comprise three phases. In Phase 1: Adaptation of outreach recruitment strategies, we will work with our project CAB, via a CBPR approach, to adapt chain-referral and credible messenger strategies for uptake of COVID-19 testing, to finalize recruitment and on-site testing protocols, and to train the CAB in the new protocols and in continuous quality improvement strategies (Aim 1). In Phase 2: Strategy Efficacy Trial and Implementation Evaluation, we will compare the two strategies in a cross-over design at two CBOs, with initial strategy assignment randomly determined and rolled out for 4 months before the cross-over occurs. The comparison of chain-referral and credible messenger strategies is not to identify the statistical superiority of one sampling strategy in providing population estimates over the other, but instead to identify the ability of each recruitment strategy to reach the target population and increase uptake of COVID-19 tests. We will examine the impact of each strategy on (i) reach (recruitment of target population), (ii) COVID-19 testing/repeat testing, and (iii) service delivery (i.e. quarantine, medical care and contact tracing) among those who test positive for COVID-19 (exploratory) (Aim 2). In Phase 3: Sustainment, CBOs will implement the strategy proven efficacious based on outcomes, and we will examine their sustainment of the program (Aim 2). Implementation evaluation will identify participant-, staff-, and organizational-level factors that influence the feasibility, acceptability, and sustainability of each strategy in these CBOs. Participants will be assessed just prior to receipt of testing. Argus and Alliance staff will be assessed before and after the roll-out of strategies (Aim 3).

We will examine the impact of the intervention on (i) reach, (ii) testing uptake and (iii) service delivery (i.e. quarantine, medical care and contact tracing among COVID-19 positive cases); and (iv) sustainability for individuals who use opioids and other drugs as well as potential mediating/moderating variables from the Andersen, SCT and EPIS models. Data drawn from Healthix on prior and future COVID-19 testing will augment study data to determine access to underserved populations and influence on future testing behavior. RAs will conduct interviews in private rooms at Argus and Alliance. Participants will be assured that responses are confidential (see Human Subjects). Interviewers will be trained with established protocols, covering informed consent, confidentiality, reporting requirements, interview content, and cultural sensitivity.

End-of-Study Definition

This study will be stopped prior to its completion if: (1) the intervention is associated with adverse effects that call into question the safety of the intervention such as increased rates of COVID-19 infection; (2) difficulty in study recruitment or retention, or enrollment of participants will significantly impact the ability to evaluate the study endpoints; (3) any new information becomes available during the trial that necessitates stopping the trial; or (4) other situations occur that might warrant stopping the trial.

Human Subjects Characteristics

Setting. Participants will be recruited from Washington Heights, Harlem two neighborhoods in northern Manhattan, the Lower East Side, a neighborhood in southern Manhattan, and the South Bronx, the locations and geographic catchment areas of Argus and Alliance. In addition to current demographics of their current

substance using clientele, we anticipate participants will comprise 64% male, 51% African American, 39% Hispanic.

Randomization. Just prior to the onset of Phase 2, the chain referral strategy will be randomly assigned (50:50) to a clinic in order to begin the first roll out. After the initial roll out and plan-do-study-act cycle (PDSA), the assignment will be switched such that the chain referral is then implemented at the other site.

Testing Participants. We anticipate enrolling n=500 participants across both strategies in an 8 month period of time. Based on demographic characteristics of the neighborhoods where recruitment will occur in addition to current demographics of the substance using clientele of Argus and Alliance, we anticipate participants will comprise 64% male, 51% African American, 28% Hispanic. Inclusion/exclusion criteria. All participants, regardless of recruitment strategy, must 1) be >18 years of age; 2) endorse opioid or other substance abuse in the past 6 months, and 3) speak English or Spanish. Those who deny history of substance use (but will be offered COVID-19 testing), or present with intoxication that prevents meaningful study participation at the time of enrollment will be excluded. Individuals too intoxicated to participate, but otherwise willing and eligible will be rescheduled up to two times. Finally, those recruited by peer chain referral (see 3.7.2) who test positive for COVID-19 will be excluded from participating in the recruitment of other individuals until such time as they receive a negative nucleic acid COVID-19 test. This more stringent assessment of non-infectiousness is being used given the likely inclusion of immunocompromised individuals in the study groups.

Agency staff and credible messengers. We will enroll n=2 staff and n=8 credible messengers across both sites. Based on current staffing demographics we anticipate staff will be 50% female, 50% Hispanic; 50% white, and credible messengers will be 63% male; 70% Hispanic; 60% White. Inclusion/exclusion criteria: staff must be 1) >18 years old; 2) employed by either Argus or Alliance

3.1.1(b) Study Procedures, Materials, and Potential Risks

Research data will be drawn from 1) self-completed questionnaires, 2) staff focus groups, 3) participant responses to process measures, 4) Healthix health data management information system, 5) analysis of saliva

Phase 2.

Staff surveys. At the beginning of Phase 2, staff and credible messengers will complete brief surveys. Guided by EPIS, Andersen and SCT, surveys will collect data on theoretically-defined inner-, outer-, and individual-level factors that may influence the implementation of the recruitment strategies and testing. Surveys will capture demographics and professional history, and attitudes and knowledge regarding COVID-19, risk reduction behaviors and testing. Surveys will be available in paper/pencil format as well online via Redcap link; surveys will be administered again at the end of Phase 2 with similar content as well as items on palatability and felt-utility of the different strategies.

Test participant surveys. Following consent and study enrollment, all participants will complete a brief assessment consisting of structured survey examining predisposing and enabling factors (e.g. mental health, substance use, social support/capital), social-cognitive factors (COVID-19 attitudes, knowledge perceived risk, stigma) and structural variables (e.g. housing security; food insecurity) and a social network inventory. A social network inventory will be adapted from previous inventories.^{1,2} The inventory will consist of a set of standard “alter generators,” which are questions asking participants to list names, pseudonyms or initials of individuals within their social networks (“alters”) who fit certain descriptions (e.g. friends, loved ones, drug sharing partners, people who provide material support, etc.). Once alters have been generated and listed in an anonymized fashion, additional questions are asked about each alter to assess their age, frequency of interaction and duration of the relationship. Participants will also be asked about alters’ drug use, as well as previous disclosures of COVID-19 exposure or seropositivity between the participant and his/her alters. RAs will conduct interviews in private rooms at either Argus or Alliance locations. At the end of this survey the participant will receive COVID-19 testing; brief follow-up interviews will occur for those participants included in the chain-referral recruitment strategy when they return to receive compensation for redeemed coupons.

Staff, credible messenger and CAB member focus group. At the end of Phase 2, interested agency staff, credible messengers and CAB members will be invited to participate in two focus groups to understand staff attitudes and perspectives on integration of each recruitment strategy and COVID-19 testing and related services into ongoing agency workflow; changes in job role, performance, or load. Staff focus groups will be run separately from CM/CAB member group and will be conducted in a private room at the home agency. The focus groups will each take approximately 1 hour to complete. Focus groups will be digitally recorded and transcribed, with the participants' consent, to facilitate the coding and analysis of these data.

Process measures: During Phase 2, participants recruited via chain-referral or credible messengers will complete a process measure, created for the study, consisting of a brief set of questions to monitor for potential ethical concerns arising among participants during the recruitment process. These questions will be defined during the intervention development process in Phase 1 and will address issues related to any unwanted disclosure of sensitive information, perceived or actual coercion or other potential psychological harms. Staff and CMs will complete a series of checklists capturing fidelity and feasibility of either recruitment method and delivery of the on-site testing.

Biological samples: During Phase 2 participants recruited via chain-referral or credible messenger will be asked to provide biological samples for COVID-19 testing, namely anterior nasal swabs for the BD Veritor™ SARS CoV 2 and Cepheid Xpert SARS CoV 2 testing platforms. Further details of the testing process can be found in Section 3.3 Testing Capacity.

Healthix (MIS) data: In Phase 2, participants will be asked to provide informed consent for disclosure of their HIPAA-protected health information (PHI) that is stored in Healthix, the large public NYC based health information exchange (HIE). Participant data drawn from Healthix will include prior and future (12m after end of Phase 2) COVID-19 test dates, location of testing, and results. This will improve our understanding of the potential unique reach of our underserved population recruitment strategy, the frequency and temporality of repeat testing, and the future impact of any project derived mitigation strategies to reduce barriers to appropriate testing in SUD populations. The inclusion of serologic test results also holds the potential of facilitating future COVID-19 vaccine initiatives, including the identification of high-risk members of the cohort without evidence of serologic immunity - if such immunity is found to be a reliable predictor of future risk.

Potential risks and risk related to the generalized global pandemic of COVID-19:

The physical risks of study participation are minimal as the biologic material that will be collected is limited to a one-time self collection of anterior nasal samples by us of nasal swabs. There is an additional minimal risk of exposure to SARS-CoV-2 associated with study participants proximity to another individual during recruitment activities and during testing, though this minimal risk will be mitigated by the use of appropriate PPE. To the extent possible, this research will be conducted in-person in coordination with in-person visits to Alliance and Argus for clinical and other related services (eg housing, vocational support) that are otherwise necessary. It will therefore involve a minimal additional risk of exposure to SARS-CoV-2 that is equivalent to the risk associated with any additional social contact between any two individuals.

There may also be several privacy-related and psychological risks associated with this study: (1) the risk a participant may reveal sensitive information about themselves; (2) the risk a participant may feel coerced into participating or may attempt to coerce others into participating during peer-recruitment; (3) the risk of contact between participants in treatment/recovery for substance use disorders and their peers who are actively using substances; (4) the risk a participant may reveal sensitive information about individuals who have not consented to be in the study; (5) the risk of an unintended breach of confidentiality; and (6) the risk of discomfort in participating in study procedures. Each of these risks is discussed below:

- 1) Participants may reveal sensitive information in this study regarding their substance use, mental health, motivation to receive treatment for substance use disorders, and relationships to members of their social networks, perceived risk of infection of COVID-19, risk reduction behaviors and social and socioeconomic impact of COVID-19. Interviews will take place in private offices at clinical sites. For all interviews, it is possible that subjects may experience feelings of distress when answering questions concerning these topics. Furthermore, some participants will be asked to recruit their peers for participation in the study. In

doing so, it is possible that sensitive information about the participant may come up as a topic of conversation with those they are attempting to recruit. This may cause feelings of distress if unexpected or unwanted.

- 2) Participants may also feel coerced into participating, believing that their decision to participate (yes/no) may affect, either positively or negatively, their ability to receive COVID-19 testing or other services. Conversely, it is also possible that during the recruitment process, participants or credible messengers might attempt to coerce others to enroll in the study.
- 3) Some participants may be engaged in treatment for substance use disorders or otherwise attempting to abstain from substance use (i.e. in recovery) at the time they engage in peer-recruitment. During the study, participants will be asked to focus recruitment on individuals they believe to be actively using substances. Therefore, it is possible that participants in recovery will have contact with peers who are actively using substances, which they would not otherwise have. Such contact may cause participants to experience cravings to return to active use.
- 4) Participants may reveal sensitive information about individuals who have not consented to participate in the study in one of two ways: a) while completing social network inventories, participants will be asked sensitive questions about their social network contacts who, in most cases, will not themselves be enrolled in the study; and b) during peer-recruitment, participants may ask social contacts about their substance use behavior, treatment access and COVID-19 risk and testing behaviors.
- 5) Staff and credible messenger participants will be asked to complete questionnaires about their organization's mission, structure, culture/climate, resources. Participants will not be asked questions that would put them at risk of criminal or civil liability or damage to financial standing, employability or reputation. Some organizational culture and climate questions, although not structured or intended to do so, could invite negative opinions critical of leaders, supervisors and/or coworkers and the risk of accidental disclosure of their responses may create discomfort for respondents or may increase the risk of repercussions to participants from supervisory staff who may be present in the focus group. In addition to being asked to complete surveys and/or to be interviewed, the work-related interactions of staff participants may be observed and other data related to quality assurance (e.g. activities that occur within Interagency work group meetings) will be collected.
- 6) Unintended breach of confidentiality may occur during the collection, storage or analysis of study data. When collecting data via the Internet for staff interviews as opposed to face-to-face, there is a risk for potential linking of work emails to study IDs, and thereby to other responses, when participants sign up for and complete the online staff survey. To an extent, these risks are mitigated by advantages with respect to data quality when collecting data via the Internet as opposed to face-to-face. Web-based surveys offer substantial advantages regarding cost and speed⁹⁶.
- 7) Finally, although unlikely, it is possible that some participants may experience emotional discomfort by the questions they are asked in the interview sessions.

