
4.2. Sample Size Determination

Power calculations assume that we will be able to recruit 500 participants in total (250 recruited in each strategy) for this supplement study over Phases 2a and 2b. We also assume alpha (type I error rate) of 0.05. Our primary outcome of interest is testing occurrence. Based on zip-code level testing data, the average baseline testing in the communities of interest (i.e., northern Manhattan, the Bronx) is 7842.2/100,000. If we assume that one of the methods of recruitment will have a testing rate similar to this baseline average, we will have > 80% power to detect an approximately 8 percentage point difference in testing among the recruitment strategies (7.8% vs. 16.1%) corresponding to an odds ratio of 2.27, a moderate effect size.

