4.5 Statistical Analyses

4.5.1 Analysis overview and main outcomes. The primary outcome of interest comparing the strategies will be testing occurrence (yes vs. no) as an indicator of testing uptake. An important secondary outcome will be reach measured through the number of coupons redeemed. Prior to the main analysis, all variables will be examined for distribution and outliers. Continuous outcomes will be described through means and standard deviations, while dichotomous and categorical outcomes will be described through proportions.

4.5.2 Statistical analysis for Aim 2. Models that compare the effect of recruitment strategy on outcomes related to reach, testing uptake, and service delivery will adjust for measures assessed at baseline (e.g., baseline substance use, testing history). For our primary (dichotomous) outcome (testing uptake) logistic regression will be used: $\text{logit}(\text{pi}) = \beta_0 + \beta_{\text{RecStr}}(\text{Recruitment Strategy})_{ii} + \beta_{\text{Site}}(\text{Site})_{ii} + \beta_{\text{SubUse}}(\text{Substance Use})_{ii} + \beta_{\text{TestHis}}(\text{Testing History})$, thus be β_{RecStr} which will estimate the differential effect of chain-referral vs. POL recruitment on testing uptake. The model will be adapted for secondary outcomes. Sensitivity analyses will stratify the analyses by time to determine if recruitment strategy effects differed before and after the cross-over. Demographic characteristics and other variables related to the Andersen, SCT, and EPIS models will be examined as potential mediators/moderators.

4.5.3 Statistical analysis for Aim 3. Implementation features related to acceptability, sustainability, feasibility, and fidelity will be assessed at both the staff- and individual-level. As an illustrative example, we will consider whether participants endorse time constraints and the association with testing uptake. The logistic model will take the form $\text{logit}(\text{pi}) = \beta_0 + \beta_{\text{RecStr}}(\text{Recruitment Strategy})_{ii} + \beta_{\text{Site}}(\text{Site})_{ii} + \beta_{\text{TimeCon}}(\text{Time Constraint})_{ii}$ where pi is the probability of being tested post-recruitment for the i^{th} individual. This model assesses the effect of a time barrier on the likelihood of getting testing while controlling for the differing recruitment strategies and sites.

4.6. Subject participation duration:

N/A

4.7. FDA regulated intervention:

No

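### With two clinics and one switch, strategy cannot be separated from a swing at one clinic in one window, and the planned logistic standard error leaves that variation out

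*Combined protocol and SAP*

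**What the plan says.** Section 3.1.1(a), under Justification for Intervention, gives the plan for Phase 2: "compare the two strategies in a cross-over design at two CBOs, with initial strategy assignment randomly determined and rolled out for 4 months". The clinics then switch. The Randomization paragraph of the same section says that "the chain referral strategy will be randomly assigned (50:50) to a clinic in order to begin the first roll out", and that after the first roll-out and a plan-do-study-act cycle "the assignment will be switched such that the chain referral is then implemented at the other site". One draw between two clinics thus fixes the whole allocation.

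Section 4.5.2 states: "For our primary (dichotomous) outcome (testing uptake) logistic regression will be used". The terms are strategy, site, substance use and testing history. There is no period term, no site-by-period or cluster term and no robust variance. Time appears only in a sensitivity analysis stratified before and after the switch.

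Section 4.2 treats participants as independent. It assumes that the study can "recruit 500 participants in total (250 recruited in each strategy"), adds "We also assume alpha (type I error rate) of 0.05", and gives the detectable contrast as "7.8% vs. 16.1%) corresponding to an odds ratio of 2.27, a moderate effect size".

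Section 4.4.1 hypothesises that chain referral is the better strategy. The Phase 3 text in Sections 3.1.1(a) and 4.1 has the clinics adopt whichever strategy is proven efficacious, and Section 4.8 plans to take it to similar organisations across the city.

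**The concern.** A randomised comparison normally relies on having enough randomised units for local disturbances to average out, with the residual spread showing up in the standard error. Here there are two units and one switch. Anything that moves testing at one clinic in one window, and not at the other, looks exactly like a strategy effect.

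The documents themselves name possible sources:
- staff turnover that cannot be addressed (Section 2.5);
- only four credible messengers per site (Section 2.5);
- a plan-do-study-act cycle between the windows (Section 3.1.1(a));
- reopening rules that tie Phase 1 visits to follow-up deemed essential by one named agency's providers (Section 3.1.2(b)).

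If such swings occur, the planned p-value is too small and the interval too narrow. The choice of strategy for Phase 3 and for scale-up would then rest on evidence that the design cannot supply.

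**Working it through.** **Inputs.** From Section 4.2: 250 per strategy, 7.8% v 16.1%, alpha 0.05. Assumed, because the documents do not say: a two-sided test, 125 people per cell, and a site-by-period standard deviation *s* in percentage points.

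**1. The plan's own figure.** The odds ratio is (0.161/0.839)/(0.078/0.922) = 2.27. SE = √(0.078×0.922/250 + 0.161×0.839/250) = 0.0288, or 2.88 points. Power ≈ Φ(8.3/2.88 − 1.96) = 82% (81.8% with a pooled variance). The stated figure of over 80% reproduces, for independent individuals.

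**2. Aliasing.** Let site 1 start with chain referral, and let y(site, window) be the cell proportions. The strategy estimate is ½[(y11 − y21) + (y22 − y12)], which is the site-by-period contrast. Intercept, site, period and strategy have rank 4 on four cells; adding site-by-period leaves the rank at 4. With period in the model, no cell-level degrees of freedom remain. The Section 4.5.2 model omits period and so leaves one, but that one is the period contrast itself, and a t test on one degree of freedom has a critical value of 12.7.

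**3. Size of a single swing.** A swing in one cell enters this estimate multiplied by ½. On the logit scale with no strategy effect and a 7.84% base rate, tripling the odds in one cell gives an apparent strategy odds ratio of √3 = 1.73 (p = 0.075) with a period term. In the planned site-only model it gives 1.94 (p = 0.027). Doubling the odds gives 1.41 and 1.48, neither significant.

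**4. The stratified analysis.** Within one window, intercept, site and strategy have rank 2 of 3, so strategy is clinic. The difference between the two window-specific effects is (y11 − y21) − (y22 − y12) = (y11 + y12) − (y21 + y22), twice the difference in site means. It therefore measures the site effect and cannot reveal the problem.

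**5. Leak from the missing period term.** With equal sites a shared shift cancels. Take sites of 200 and 300, each split evenly over the windows, and a period odds ratio of 2. Weighting the sites 0.4 and 0.6, the log odds ratio for strategy is about (0.6 − 0.4)×ln 2 = 0.139, an odds ratio of about 1.15. The fitted site-only model gives 1.145. With a period term it is 1.00.

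**6. Type I error.** Independent cell deviations add ¼ × 4s² = s² to the variance. At a common 7.8%, SE = √(2×0.078×0.922/250) = 2.40 points. The true error of the nominal 5% test is 2[1 − Φ(1.96×2.40/√(2.40² + s²))]:

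| s (points) | Type I error |
|---|---|
| 0 | 5% |
| 1 | 7% |
| 2 | 13% |
| 3 | 22% |

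Simulation on the logit scale agrees. With cell SDs of 0.3 and 0.4 around 7.84%, the site-only model rejects a true null 13.7% and 20.7% of the time; for comparison, s = 2 points is 0.02/(0.078×0.922) = 0.28 on that scale. A period term barely changes this (13.5% and 18.9%).

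**7. Tipping point.** An observed 8.3-point difference loses significance when √(2.88² + s²) = 8.3/1.96 = 4.23, so s = √(4.23² − 2.88²) ≈ 3.1 points.

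**8. Power at the planned difference.** If s were known and included, power would be Φ(8.3/√(2.88² + s²) − 1.96) = 66% at s = 2 and 51% at s = 3. The planned test, which ignores s, would reject with probability Φ((8.3 − 1.96×2.88)/√(2.88² + s²)) = 78% and 74%.

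**The case against.** The strongest reply is that no value of s is documented and that only differential swings matter. City-wide changes in the pandemic reach both clinics at once and cancel when the clinics are balanced. In addition, participants are offered a test straight after one assessment (Sections 2.5 and 3.1.1(b)), so shocks to community testing may not carry over to the outcome among people already enrolled. Both points are fair, and they are why the figures are a range starting at s = 0. They do not show that s is zero, and the four cells cannot show it either. Cancellation of shared shifts also needs clinics of equal weight, because the model has no period term. Nor is a higher testing rate reassuring: in the simulation at a 50% base rate, a logit SD of 0.2 gives 20% type I error, against 8.7% at 7.84%.

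A second reply is that Section 3.1.1(a) disclaims any search for statistical superiority. That sentence concerns sampling strategies for population estimates. Sections 4.2 and 4.4.1 still power and test a comparative hypothesis.

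A third is that the stratified analysis already yields the four proportions. It could, and they should be reported as such, but it leaves the aliasing where it is. An interval over an assumed s adds no information from the data; it only shows how much local variation the conclusion can bear.

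**Conclusion.** The point stands. Strategy is aliased with site-by-period by design, the planned standard error excludes that variation, and the planned sensitivity analysis cannot detect it. Under the assumed s, type I error is about 13% at 2 points and 22% at 3, and an 8.3-point result is fragile to s of about 3.1 points. Separately, the missing period term lets shared shifts leak in when the clinics enrol unequally.

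A reader might infer more, and the documents do not support it:
- **That a local swing passes into the estimate in full.** It enters the balanced contrast at half size.
- **That planned power collapses.** The 66% and 51% belong to a test with s known. The planned test would still reject 78% and 74% of the time; its fault is the inflated type I error.
- **That the planned test is invalid outright.** At s = 0 it is valid apart from the period leak, and the documents give no s.
- **That a period term settles the matter, or is useless.** It removes the shared-shift leak and leaves the local swings.

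Dependence within referral chains or within messengers is a separate matter and is not assessed here.

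**What to change.** In Section 4.5.2:
1. Add a period term to the primary model.
2. Report the four site-by-period testing proportions with their denominators.
3. Give the strategy confidence interval with SE² = model SE² + s² over a stated range of s, and the s at which significance is lost.
4. State that the comparison applies to these two clinics in these windows.

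In the Phase 3 text of Sections 3.1.1(a) and 4.1, replace the wording that a strategy has been proven efficacious with, for example, the strategy with the better observed outcomes.

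More clinics or more switches would address the cause. But Section 2.6 lists the study as not recruiting and Table 1 shows 486 enrolled, so the remedy has to lie in analysis and reporting. It needs no new data and only a few lines of text. The cost is a wider interval and a more modest claim.
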